- 6. To be performed at the following timepoints in the mornings only: pre-dose, and 0.25, 0.5, 1, 4 h post-dose
- 7. To be performed at the following timepoints in the mornings only: pre-dose and 4 h post-dose
- 8. ECG and vital signs to be obtained 2 h after the morning dose
- 9. BID

2016N290366_02 **CONFIDENTIAL**

10. PK samples on days 1, 3, 6, and 19 will be collected at the following timepoints: pre-dose, 0.25, 0.5, 0.75, 1, 2, 4, 6, 8, 10, 12 h. On day 2, one sample in the morning (24h post day 1 dose). On days 4 and 5, one sample on each morning (24h and 48h post day 3 dose). On days 6 and 19, the evening dose will be given after 12 h post-dose sample is collected. On all other days, PK sample will be collected once, before the morning dose (if on dosing days).

205822

Schedule for Cohort A Part 2 (and all other single dose administrations)

				Т	reatme	nt Period	, Days	(D) and	l hours (h)							
	D-1						D.	1									
Procedure		Pre- dose	0h	0.25h	0.5h	0.75h	1h	2h	4h	6h	8h	10h	12h	24h			
Inclusion and exclusion criteria	Х																
Brief physical examination, oral examination	Х													Χ			
Substance testing (drugs, alcohol)	Х																
Serum pregnancy test in women	Х																
Admittance to clinic	Х																
Inhaler device training ¹	Х																
Randomization	X2																
Discharge														X3			
Haematology, clinical chem and urinalysis (include liver chem) ⁴	Х													Χ			
Spirometry		X ⁵		X ⁶	Χ		X6		X ₆								
Telemetry			30 r	nin pre-d		d continu		il at lea	st 4 h								
12-lead ECG and vital signs		XXX		Х			Χ	Χ	Х		Χ		Χ				
CCI15106-IP or placebo treatment			Χ														
PK blood sample ⁷		Х		Х	Χ	Х	Χ	Χ	Х	Χ	Χ	Χ	Χ	Χ			
AE review		← =	=====	======	=====	=====	=====	=====	=====	=====	=====	=====	=====	\rightarrow			
SAE review	←====	=====			=====			=====	=====		=====		=====	==>			
Concomitant medication review	←====	=====			=====				=====		=====		=====	==>			

- 1. Day -1 inhaler training may be done on Day 1 instead, before the first dose administration. Other time-points may be added per investigators discretion
- 2. Can be performed on Day 1 prior to dosing
- 3. After all assessments are completed
- 4. To be drawn fasting (for at least 8 h)
- 5. To be performed within 15 to 60 minutes pre-dose
- 6. To be performed after ECG, VS and PK blood draw are obtained
- 7. Additional PK collection time points may be added to better characterize the PK profile

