5. STUDY DESIGN

5.1. Overall Design

This is a two-part, double-blind (sponsor unblind), randomized, placebo-controlled, single and repeat escalating dose study. Investigator and participants will be blinded to treatment type (active or placebo), but will know what dose of the medication is being administered. Part 1 will investigate single and repeat ascending doses in healthy participants and investigate environmental and bystander exposure. Part 2 will evaluate single and repeat dose in participants with moderate COPD. Participants may only be enrolled in one study part and randomized to one cohort per the randomization schedule.

Study schematic is presented below:

Part 1 Healthy Participants

[figure not shown]
Cohort A: 8 participants (6 active; 2 placebo)

Cohort B: 14 participants (12 active; 2 placebo)

Cohort C: 14 bystanders for environmental exposure, to be run concomitantly with Cohort B

[figure not shown]

Part 2 Participants with COPD

[figure not shown]
Cohort A: Single dose; 8 participants (6 active; 2 placebo)

Cohort B: Multiple dose; 14 participants (12 active; 2 placebo)

The following reviews will be conducted during the study progression:

- In Part 1, Cohort B dosing can begin only after review of safety/tolerability and PK of all dosing in Part 1 Cohort A (see Section 7.2 for composition of the review team).
- In Part2, Cohort A dosing can begin only after review of safety/tolerability and PK for a single dose administration of 60 and 120 mg in all participants in Part 1 Cohort A (see Section 7.2 for composition of the review team).
- In Part 2, Cohort B dosing can begin only after the comprehensive review of all data obtained in Part 1, including safety and systemic PK, as well as lung PK where available (see Section 7.2 for composition of the review team) and after review of safety/tolerability of Part 2 Cohort A.
- Environmental and bystander exposure review may be conducted at any time after the data are collected. Until this review is completed and exposure found acceptable, all subsequent cohorts will be dosed in the negative pressure environment.
- The planned doses may be modified, repeated or cancelled based upon safety/tolerability/ and/or PK from preceding cohorts (See Section 7.2 for more information). Single doses will not exceed 120 mg and repeat doses 60 mg BID.

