5.4. Scientific Rationale for Study Design

Participants and all site personnel, with the exception of the study pharmacist or designee, will be blinded to participant randomization throughout the study. The GSK study team participating in the dose escalation meetings will review blinded data and will be un-blinded on a need to know basis only if necessary to facilitate review of the safety, tolerability and PK data as appropriate in real time to inform dose escalation decisions. The GSK study team or personnel at any contract research organization that may be involved in data management or in statistics and programming will not reveal the treatment assignments to the site personnel or participants.

In repeat dosing cohorts, CCI15106-IP will be administered for 14 days to mimic the expected duration of treatment in target patient populations.

Inclusion of Bronchoscopy

BAL will be performed on 14 healthy participants (Cohort B Part 1) and 14 participants with COPD (Cohort B Part 2) to evaluate levels of CCI15106 in the ELF. BAL will be performed once, as soon as possible (within 1h) after the first (morning) dose. This will allow assessment of CCI15106 levels at around tmax in the ELF. The timing of BAL in Part 2 Cohort B may be adjusted based on BAL results obtained in Part 1. Available models [Weber, 2017] predict that the level of CCI15106 in the bronchoalveolar fluid following 14 days of 60 mg BID dosing may be achieved above 200 μ M around T_{max} which is above the EC50 for all respiratory viruses including HRV and expected to prevent or minimise the migration of an upper respiratory tract viral infection to the lower respiratory tract. These data will enable a more accurate estimation of the dose to lung exposure ratio and provide valuable information for future dose predictions.

Inclusion of Participants with COPD Cohort

Due to potential exposure differences as a function of COPD-induced lung damage, participants with moderate COPD will be included to aid in dose selection for the future proof of concept studies in participants with COPD. This cohort will also help obtain some safety and tolerability data in this patient population prior to a wider administration in the Proof of Concept study.

Inclusion of Bystander Cohort

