5.5. Dose Justification

The dose proposed for Part 1 Cohort A is based on the data from 202031 where CCI15106-CFI up to 60 mg single dose has been evaluated, and no SAEs or severe AEs were observed, as well as the investigation of the four week toxicity and toxicokinetics in rats and dogs in which the NOAEL was determined [GSK Document Number 2017N312240 00 and GSK Document Number 2017N312247 00].

Table 1 below shows the safety margins in terms of lung and systemic exposure with respect to the NOAEL obtained from the pre-clinical studies, and the folder cover with respect to the systemic exposure following oral administration of the marketed dose (1200 mg/day) in humans for the doses proposed in this study. These data indicated reasonable safety margins for Cohort A in Parts 1 and 2, where single dose of CCI15106-IP will be administered.

The selection of appropriate dose for Part 1 Cohort B will be performed upon consideration of available safety, tolerability and systemic PK data from Part 1 cohort A. The review data set for this selection will, at minimum, consist of: any adverse events, liver function test results, vital signs, ECG, spirometry data, and laboratory findings, and any available systemic PK results.

The selection of appropriate dose for Part 2 Cohort A will be performed upon consideration of available safety and tolerability data following the single doses (60 and 120 mg) in all participants in Cohort A of Part 1.

The selection of appropriate dose for Part 2 Cohort B will be performed upon consideration of available safety, tolerability, systemic PK and lung concentration data from Part 1 Cohort B.

The dose level in any cohort may be titrated up or down based on emerging safety, tolerability, and systemic PK and lung data where available. The maximum dose will not exceed 120 mg per day.

Table 1 Prediction of Human Systemic and Lung Exposure and Safety Margins of CCI15106

Dose Frequency Assume 100%	Proposed human dose per day (mg)	Human Lung Dose (mg/g) on in humar	Lung Safety Margin (Rats)	Lung Safety Margin (Dogs)	Human Systemic expoure AUC(0-24) (ng.h/mL) *	Systemic Safety Margin (Rats)	Systemic Safety Margin (Dogs)	Systemic Safety Margin (human Oral Ribavirin)
SD	60	0.06	12	16				
SD	120	0.12	6	8				
Assume 59% lung deposition in humans								
SD	60	0.04	20	26	552	17	40	92
SD	120	0.07	10	13	1104	8	20	46
BD**	30	0.04	20	26	3080	3	7	16
BD	60	0.07	10	13	6150	2	4	8

Assumptions:

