7.2. Dose Modification

- This protocol allows some alteration from the currently outlined dosing schedule.
 The maximum daily dose administered will not exceed 120 mg per day either as a single dose or as 60 mg BID.
- The decision to proceed to Part 1 Cohort B will be made by the GSK Study Team comprised at a minimum of the team leader, medical monitor, Global Clinical Safety and Pharmacovigilance scientist or physician (Clinical Pharmacokineticist, Statistician and Preclinical Safety Assessment as necessary), and the Investigator or delegate based on safety and tolerability data obtained in all participants at the prior dose levels in Part 1. The actual doses to be administered may be adjusted based on safety, tolerability, and preliminary PK data if appropriate, at previous dose levels; these dose adjustments may involve either an increase or a decrease in the planned dose. The highest dose in the study will not exceed 120 mg per day either as a single dose or as 60 mg BID.
- The decision to proceed to participants with COPD will be made by the GSK Study Team comprised at a minimum of the team leader, medical monitor, Global Clinical Safety and Pharmacovigilance scientist or physician (Clinical Pharmacokineticist, Statistician and Preclinical Safety Assessment as necessary), and the Investigator or delegate based on safety and tolerability data obtained after single dosing completes in healthy participants in Part 1 Cohort A.
- The actual doses to be administered may be adjusted based on safety, tolerability, and preliminary PK data if appropriate, at previous dose levels; these dose adjustments may involve either an increase or a decrease in the planned dose.
- The dosing schedule may also be adjusted to expand a dosing cohort to further evaluate safety and PK findings at a given dose level, or to add cohorts to evaluate additional dose levels. The study procedures for these additional participant(s) or cohort(s) will be the same as that described for other study participants.

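### COPD repeat dosing at 60 mg BID can start without any review of the COPD single-dose PK already collected in Part 2 Cohort A

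*Protocol*

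**What the plan says.** Section 5.1 sets three conditions that must be met before a later cohort is dosed.

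- **Part 1 Cohort B (healthy, repeat dose):** review of safety, tolerability and PK of all Part 1 Cohort A dosing.
- **Part 2 Cohort A (COPD, single dose):** "In Part2, Cohort A dosing can begin only after review of safety/tolerability and PK for a single dose administration of 60 and 120 mg" in the healthy Part 1 Cohort A participants.
- **Part 2 Cohort B (COPD, 60 mg BID, 14 days):** review of all Part 1 data, including systemic PK and any available lung PK, "and after review of safety/tolerability of Part 2 Cohort A".

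Section 5.5 says that selection of the Part 2 Cohort B dose is "performed upon consideration of available safety, tolerability, systemic PK and lung concentration data from Part 1 Cohort B". Section 7.2 describes no separate decision on Part 2 Cohort B. Its decision to enter COPD participants rests on "safety and tolerability data obtained after single dosing completes in healthy participants in Part 1 Cohort A".

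The Schedule of Activities for Cohort A Part 2 has PK samples from pre-dose to 24 h, with the note "Additional PK collection time points may be added to better characterize the PK profile".

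Section 5.4 includes COPD participants "Due to potential exposure differences as a function of COPD-induced lung damage", and gives the purpose as "to aid in dose selection for the future proof of concept studies in participants with COPD".

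Section 5.1 also has a permissive clause: "The planned doses may be modified, repeated or cancelled based upon safety/tolerability/ and/or PK from preceding cohorts". Sections 5.5, 7.2 and 10.3.4 contain similar optional wording.

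**The concern.** The other two start conditions in Section 5.1 name the PK of the cohort under review. Part 2 Cohort A is the only preceding dosing cohort whose PK is not named, and it is also the only one with COPD. The site and sponsor could start 60 mg BID in COPD participants, fully compliant with the protocol, without having looked at a COPD concentration.

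The protocol itself expects that exposure may differ in damaged lungs. It states this to support later proof-of-concept dosing, but the same difference would apply to Cohort B. If the difference were a large increase in absorption or bioavailability, it would first be seen in the 12 active COPD participants on repeat dosing. Good tolerability after a single dose says little about this, because predicted exposure on Day 14 is several times higher than after one dose.

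**Working it through.** **1. Table 1 margins at 60 mg BID, reproduced.** Inputs from Section 5.5: predicted human AUC(0-24) on Day 14 of 6150 ng.h/mL; rat NOAEL AUC 9.34 µg.h/mL; dog NOAEL AUC 22.2 µg.h/mL; steady-state oral ribavirin AUC(0-24) 50.722 µg.h/mL. Margin = reference AUC / predicted human AUC.

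- Rat: 9340 / 6150 = 1.52 (printed 2)
- Dog: 22200 / 6150 = 3.61 (printed 4)
- Oral ribavirin: 50722 / 6150 = 8.25 (printed 8)

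The printed figures are correct as whole numbers, but rounding hides how thin the rat margin is.

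**2. Single dose against Day 14.** Table 1 predicts 552 (60 mg) or 1104 (120 mg) ng.h/mL after a single dose. At the same daily dose, 6150 / 1104 = 5.57, so tolerability in Part 2 Cohort A is observed at under a fifth of the later predicted exposure.

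**3. Margins if COPD bioavailability is higher.** The protocol gives no COPD:healthy ratio, so these values are illustrative and assume linear PK. Each margin is divided by the ratio.

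| Ratio | Rat | Dog | Oral |
|---|---|---|---|
| 1 | 1.52 | 3.6 | 8.2 |
| 1.25 | 1.21 | 2.9 | 6.6 |
| 1.5 | 1.01 | 2.4 | 5.5 |
| 2 | 0.76 | 1.8 | 4.1 |

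**4. What the added check can show.** The comparison is 6 active COPD participants (Part 2 Cohort A) against 6 active healthy participants (Part 1 Cohort A). The between-participant CV is assumed. With s = √ln(1 + CV²), SE of the log ratio = s√(2/6), and the 95% CI factor is exp(2.228 × SE) on 10 degrees of freedom. Probabilities use the normal distribution of the log ratio.

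| CV | SE | CI factor | P(obs > 1.5), true 2 | P(obs > 1.5), true 1 | P(obs > 1.25), true 1 |
|---|---|---|---|---|---|
| 20% | 0.114 | 1.29 | 99% | 0.02% | 3% |
| 30% | 0.169 | 1.46 | 96% | 1% | 9% |
| 40% | 0.222 | 1.64 | 90% | 3% | 16% |

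The check can reveal a large difference but not a small one.

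**5. What it cannot show.** Reduced renal clearance is a different mechanism. As a simplification, take a one-compartment bolus model and choose the elimination rate k so that the Day 14 to single-dose ratio equals 5.57. This gives k = 0.0075/h, a half-life of about 93 h. Dividing clearance by 1.5 then raises steady-state AUC 1.5-fold and Day 14 AUC about 1.32-fold, because steady state is not reached by then. It raises single-dose AUC(0-24) only 1.03-fold and the 24 h concentration only 1.06-fold. A 24 h single-dose profile would miss it.

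**6. Carry-over in the healthy comparator.** Part 1 Cohort A receives 60 mg on Day 1 and 120 mg on Day 3. In the same model the Day 1 dose adds 0.5 × exp(−48k) = 0.35 of the 120 mg AUC(0-24). An uncorrected COPD:healthy ratio at 120 mg would be about 1 / 1.35 = 0.74 of the true one. The Part 2 Cohort A dose is in a figure not reproduced in the text available, so this applies only if that dose is 120 mg.

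**The case against.** The strongest reply is that the protocol already provides everything needed. Sections 5.1, 5.5, 7.2 and 10.3.4 let doses be changed, or PK evaluated, on emerging data. Sections 5.4 and 7.4 allow unblinding for real-time review and give the pharmacokineticists the randomization codes. A sensible team would look at the COPD PK. This is true, but every one of these clauses is optional. Section 5.1 makes PK review compulsory at its other two steps and leaves it out here.

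Second, the Section 5.5 sentence is not a full list of what must be reviewed. It also omits COPD safety, which Section 5.1 does require. That is fair: the binding text is the Section 5.1 bullet, and Section 5.5 only repeats the omission.

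Third, Section 5.4 speaks of differences, not increases, and the consequence is modest. Even at 2-fold, exposure stays 4.1-fold below marketed oral ribavirin. The rat NOAEL comes from 4 weeks of dosing against 14 days here. The 120 mg/day cap, the Section 8.1.3 stopping and halt rules, Day 7 laboratory tests and repeated spirometry all apply. This stands, and it limits the weight of the point.

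Fourth, the check would miss reduced clearance, although Section 3.3.1 describes ribavirin as substantially renally excreted and COPD participants are excluded only below an eGFR of 30. This also stands, and it restricts how the result may be used.

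**Conclusion.** The point holds. The mandatory review before COPD repeat dosing requires PK from healthy participants only, and no clause makes the COPD single-dose PK a condition of starting. A COPD exposure about 52% above prediction would use up the rat systemic margin of 1.52 at 60 mg BID. The margin to marketed oral ribavirin would remain well above 1 at every ratio considered.

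The added review would be informative for large differences in absorption or bioavailability and uninformative for small ones or for reduced clearance. The margins follow from Table 1. The COPD:healthy ratios, the CV of 20–40% and the one-compartment model are assumptions. The existing protections make this a worthwhile and inexpensive improvement, not a serious safety gap.

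**What to change.** In the Section 5.1 bullet on Part 2 Cohort B, add *and systemic PK* to what is reviewed from Part 2 Cohort A. In Section 5.5, name Part 2 Cohort A alongside Part 1 Cohort B as the basis for the dose.

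The following would help the review but are optional detail:

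- Compare COPD Cmax, AUC(0-24) and the 24 h concentration with Part 1 Cohort A at the same single dose, listed with each participant's baseline eGFR.
- If that dose is 120 mg, correct the healthy Day 3 values for the pre-dose concentration.
- Use the result to look for large absorption or bioavailability differences. Do not scale the healthy repeat-dose AUC by the single-dose ratio as if it were the steady-state ratio; treat it at most as a lower bound.

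The cost is a change to two sentences and a possible short delay to Part 2 Cohort B while samples already scheduled from 8 participants are assayed. Part 2 Cohort B must in any case wait for all Part 1 data, so the assays may overlap with that wait. No new samples, procedures or participants are needed.

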6. STUDY POPULATION

Prospective approval of protocol deviations to recruitment and enrollment criteria, also known as protocol waivers or exemptions, is not permitted.

6.1. Inclusion Criteria

6.1.1. Inclusion Criteria for Healthy Participants and Bystanders

Participants are eligible to be included in the study only if all of the following criteria apply. Rescreening is allowed only if approved by the Medical Monitor.

Age

1. Participant must be 18 to 65 years of age inclusive, at the time of signing the informed consent.

^{*} human systemic AUC(0-24) is predicted from a mechanistic model [Weber, 2017]

^{**} BD - twice daily dosing; AUC(0-24) on Day 14

Type of Participant and Disease Characteristics

- 2. Participants who are overtly healthy as determined by medical evaluation including medical history, physical examination, laboratory tests, and cardiac monitoring.
- 3. A participant with a clinical abnormality or laboratory parameter(s) which is/are not specifically listed in the inclusion or exclusion criteria, outside the reference range for the population being studied may be included only if the investigator (in consultation with the Medical Monitor if required) decide and document that the finding is unlikely to introduce additional risk factors and will not interfere with the study procedures.

Weight

4. Body weight ≥50 kg for males and 45 kg for females and body mass index (BMI) within the range 19 to 31 kg/m² (inclusive) for males and 17 to 31 kg/m² (inclusive) for females

Sex

5. Male OR Female

a. Male participants:

A male participant with female partner of child bearing potential must agree to use contraception as detailed in Appendix 5 of this protocol during the treatment period and for at least 7 months after the last dose of study treatment and refrain from donating sperm during this period.

b. Female participants:

A female participant is eligible to participate if she is not pregnant (see Appendix 5), not breastfeeding, and not a woman of childbearing potential (WOCBP) as defined in Appendix 5.

Informed Consent

6. Capable of giving signed informed consent as described in Appendix 3 which includes compliance with the requirements and restrictions listed in the informed consent form (ICF) and in this protocol.

6.1.2. Inclusion Criteria for Participants with COPD

Participants are eligible to be included in the study only if all of the following criteria apply:

Age

1. Participant must be 40 to 75 years of age inclusive, at the time of signing the informed consent.

Type of Participant and Disease Characteristics

- 2. Diagnosed with moderate COPD (GOLD class II) by a qualified physician as defined by the GOLD guidelines (http://www.goldcopd.org/).
- 3. The participant has spirometry at screening, conducted 15-30 minutes after administration of 400 microgram (µg) salbutamol via metered dose inhaler showing:
 - post-bronchodilator forced expiratory volume in 1 second (FEV₁)≥50% and <80% predicted normal [Quanjer, 2012] and
 - post-bronchodilator FEV₁/ forced vital capacity (FVC)<0.7, where FEV₁ is forced expiratory volume in 1 second and FVC is forced vital capacity.
- 4. Participant is a smoker or an ex-smoker with a smoking history of at least 10 pack years (1 pack year = 20 cigarettes smoked per day for 1 year or equivalent).
- 5. A participant with a clinical abnormality or laboratory parameter(s) which is/are not specifically listed in the inclusion or exclusion criteria, outside the reference range for the population being studied may be included only if the investigator in consultation with the Medical Monitor if required agree and document that the finding is unlikely to introduce additional risk factors and will not interfere with the study procedures.

Weight

6. Body weight \geq 45 kg and BMI within the range 17 – 34 kg/m² (inclusive), unless morbidly obese.

Sex

7. Male OR Female

c. Male participants:

A male participant with female partner of child bearing potential must agree to use contraception as detailed in Appendix 5 of this protocol during the treatment period and for at least 7 months after the last dose of study treatment and refrain from donating sperm during this period.

d. Female participants:

A female participant is eligible to participate if she is not pregnant (see Appendix 5), not breastfeeding, and not a WOCBP as defined in Appendix 5.

Informed Consent

8. Capable of giving signed informed consent as described in Appendix 3 which includes compliance with the requirements and restrictions listed in the informed consent form (ICF) and in this protocol.

